12.1.2. Primary Effectiveness Endpoints: Proportion of LV MSP Group with an Improved CCS

The effectiveness endpoint for SMART MSP PAS is the proportion of the LV MSP Group with an Improved CCS. Details regarding the CCS are provided in **Section 11.5.1**. For this endpoint, those subjects in the LV MSP Group that become responders will be defined as having an Improved CCS as discussed in **Section 11.5.1**. This endpoint will be evaluated at the 12 Month Visit to determine if the LV MSP Group subjects improved from their 6 Month Visit.

12.1.2.1. Hypotheses

The following hypotheses will be used to evaluate the Primary Effectiveness Endpoint:

H_0 : Proportion of LV MSP Group subjects with Improved CCS from 6 Month Visit through 12 Month Visit $\leq 5\%$

H_A : Proportion of LV MSP Group subjects with Improved CCS from 6 Month Visit through 12 Month Visit $> 5\%$

12.1.2.2. Sample Size

The sample size of 110 subjects with paired CCS calculation from the 6 Month Visit through 12 Month Visit is required to evaluate the Primary Effectiveness Endpoint. For further details on overall sample size and attrition see **Figure 12.3-1**. The overall study sample size is

driven by the primary effectiveness endpoint. This sample size was calculated based on a one-sided exact test for a single binomial proportion, using SAS Version 9.4 with the following assumptions:

- Performance goal = 5%
- Expected performance = 15%
- One-sided significance level = 5%
- Power = 95%

The performance goal was established based on the evaluation of clinical response data previously reported for similar features under investigation, and based on clinical input from the study's National Principal Investigator and the Steering Committee that an improvement of at least 5% would be clinically meaningful given the subject's non-responder status as determined after 6 months of conventional CRT with single-site LV pacing.

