12.1.2.3. Statistical Methods

The SMART MSP PAS study's Primary Effectiveness Endpoint will be analyzed when the last 12 Month Visit is completed by the subjects in the LV MSP Group. Subjects eligible for this analysis include all non-responder subjects who meet the definition of the LV MSP Group. The LV MSP Group subjects' CCS data (NYHA class, HF event, all-cause mortality, and patient global assessment) will be collected at the 6 and 12 Month Visit and contribute to the endpoint analysis. The LV MSP Group subjects with the LV MSP on for less than 6 month duration will be included in the analysis.

The 95% one-sided lower pointwise confidence limit of the response rate will be calculated using the one-sided exact methodology for a single binomial proportion and compared to the performance goal of 5%. If the lower confidence limit exceeds the performance goal, then the null hypothesis will be rejected.

Subjects that do not have complete paired CCS data regarding NYHA class, HF event, all-cause mortality, and patient global assessment collected at the 6 and 12 month follow-up visit will be considered to have missing data. A tipping point analysis will be used to determine the potential effects subjects with missing data could have had on the results. The tipping point analysis will consider a range of possible responder rates in the subjects with missing data. The tipping point will be determined by the point at which the endpoint results turn from passing (null hypothesis rejected) to failing (null hypothesis not rejected).

12.2. *Ancillary Assessments*

The ancillary assessments are not formal endpoints and are not statistically powered.

12.2.1. Assessment of Echocardiographic Measurements and CCS Response Status Outcomes in Non-responders

Subjects with echo measurements (such as LVEF and LVESV) at Enrollment, 6, and 12 Month Visit will be reported. In addition, data available (response outcome of CCS and echo

measurements) for these subjects will be reported with summary descriptive statistics and listings. Additional analyses may be explored.

12.2.2. Assessment of Effectiveness of LV MSP in the SMART MSP PAS and SMART Registry

A supplemental analysis of the primary effectiveness endpoint and subgroups will be performed and include a subset of data collected from the SMART Registry, a post market study assessing the LV MSP feature in a similar patient population to fulfill the requirement of an European regulatory body.

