12.4.4. Control of Type I Error

Each primary endpoint can be tested at the significance level of 5% while still maintaining the overall type I error level at no greater than 5%. This follows the methodology of the Intersection-Union Test (IUT).

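### The 110 evaluable subjects for the effectiveness endpoint do not follow from the stated inputs: at one-sided 5% they give 97.6% power, and 95% needs only 93 to 102

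*Combined protocol and SAP*

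**What the plan says.** Section 12.1.2.2 states: "The sample size of 110 subjects with paired CCS calculation from the 6 Month Visit through 12 Month Visit is required" for the primary effectiveness endpoint. It attributes the number to a "one-sided exact test for a single binomial proportion, using SAS Version 9.4" and lists four inputs: "Performance goal = 5"%, "Expected performance = 15"%, "One-sided significance level = 5"%, and power of 95%.

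The planned analysis uses the same level. In section 12.1.2.3, "The 95% one-sided lower pointwise confidence limit of the response rate will be calculated using the one-sided exact methodology", and the endpoint passes if that limit is above the goal. Section 12.4.4 adds: "Each primary endpoint can be tested at the significance level of 5"%.

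Sections 12.1.1.2 and 12.3 say that this endpoint drives the total enrolment of 586. Attrition is handled separately in section 12.3, after the 110 has been fixed.

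**The concern.** The size is presented as the output of a named test with listed inputs, so it should be reproducible from them. It is not. Section 12.1.2.2 mentions no rounding or safety margin, and attrition cannot explain the gap because it is applied in going from 110 evaluable to 586 enrolled.

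The level, power and size of the primary effectiveness endpoint are the figures a regulator or later reader will try to reproduce first, and the enrolment target rests on them. A size that does not match its inputs raises two questions: was the study sized under a different level from the one used in the analysis, and is its power really the figure stated? The second can be answered from the document. The first cannot be settled without the sponsor.

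**Working it through.** **Inputs.** From section 12.1.2.2: p0 = 0.05, p1 = 0.15, one-sided α = 0.05, target power 0.95, n = 110, exact binomial test. The analysis level is confirmed in sections 12.1.2.3 and 12.4.4.

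**Formula.** For each n, take the smallest r with P(X ≥ r | n, p0) ≤ α. The attained level is that tail probability, and power is P(X ≥ r | n, p1). Rejecting at r or more is equivalent to the exact one-sided lower limit exceeding 5%.

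**Attempt to reproduce 110 at the stated level (one-sided 5%).**

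| n | r | attained level | power |
|---|---|---|---|
| 92 | 9 | 0.0408 | 0.9462 |
| 93 | 9 | 0.0432 | 0.9504 |
| 96 | 10 | 0.0219 | 0.9252 |
| 101 | 10 | 0.0299 | 0.9490 |
| 102 | 10 | 0.0318 | 0.9529 |
| 110 | 10 | 0.0492 | 0.9756 |
| 111 | 11 | 0.0234 | 0.9555 |

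Exact power moves in a sawtooth because r is an integer, so there are two usual definitions of the required size. The smallest n reaching 95% is 93. The smallest n from which power never drops below 95% again is 102. Neither is 110. Power at 110 is 97.6%, 2.6 percentage points above the stated figure.

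**Other formulas at one-sided 5%.** The normal approximation for 95% power gives 90, or 100 with continuity correction. The Wald formula with the variance at p1 gives 138 for 95% power. It rounds up to 110 only at 90% power, which is neither the stated test nor the stated power.

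**Same calculation at one-sided 2.5%.**

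| n | r | attained level | power |
|---|---|---|---|
| 109 | 11 | 0.0208 | 0.9481 |
| 110 | 11 | 0.0221 | 0.9519 |
| 113 | 12 | 0.0111 | 0.9301 |
| 118 | 12 | 0.0153 | 0.9512 |

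Here 110 is the smallest n reaching 95%. Under the stricter definition the answer would be 118.

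**Check against the safety size.** Section 12.1.1.2 uses the same kind of test (90% against 98%, 5% level, 80% power) and gives 61. At one-sided 5%, n = 60 has power 66.2% and n = 61 has 87.7%, so 61 is the smallest n reaching 80%. It reproduces at the stated level; at 2.5% the smallest n would be 70. The same smallest-n convention at 5% gives 93 for effectiveness.

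**Scale of the gap.** 110 − 102 = 8 and 110 − 93 = 17 evaluable subjects. By simple proportion, 586 × 93/110 = 495.4 and 586 × 102/110 = 543.4, or about 496 to 544 enrolled after rounding up.

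**Dependence of the pass mark on n.** With 10 Improved of 110 the 95% one-sided lower limit is 5.015%, which passes. With 10 of 111 it is 4.97%, which fails.

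**The case against.** The strongest reply is that nothing goes wrong. The listed 95% can be read as a floor, and 110 meets it. The plan does the same for safety, where 80% is listed and 61 subjects give 87.7%. Type I error is held at 4.92% and the analysis rule is unaffected. All of this stands, and it limits the point to a correction of the text. It does not rescue the derivation, though. The safety size is the smallest that meets its target, so its excess power comes from the discreteness of the test. The effectiveness size is 8 to 17 above the smallest that meets its target, and no reason is given.

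A reader might infer that the study was sized at one-sided 2.5%, and that the error rate and pass mark are therefore in doubt. The document does not support that. It states 5% for the sizing, the confidence limit and the type I error control alike, and 2.5% appears nowhere. The numerical match holds only under the smallest-n convention, since power at 2.5% falls to 93.0% at n = 113. There is also an explanation within 5%: 110 is the last n with a critical count of 10, so it is a local peak of power, and the first such peak once power stays above 95%. The document does not give that reason either. The match is worth a question to the sponsor, not a conclusion.

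**Conclusion.** The point stands as a correctable inconsistency in section 12.1.2.2. With the stated test, rates and one-sided 5% level, 110 is not the required size and 95% is not its power. The required size is 93 or 102, depending on how the sawtooth is treated, and 110 gives 97.6%.

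The discrepancy is in the safe direction. The study is not underpowered, the type I error is controlled, and the decision rule in sections 12.1.2.3 and 12.4.4 is unambiguous. The cost of leaving it is a primary-endpoint calculation that cannot be reproduced, and an evaluable target 8 to 17 subjects above what its inputs require.

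The power figures assume the exact binomial test as stated, a true rate of 15%, and exactly the evaluable number shown. The enrolment equivalents also assume that the attrition in section 12.3 scales proportionally. Why 110 was chosen cannot be determined from the document.

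**What to change.** Keep 586 enrolled, 110 evaluable and the confidence-limit rule in section 12.1.2.3. Reword section 12.1.2.2 to say that, with the one-sided exact test at 5% and rates of 5% and 15%, 110 evaluable subjects give about 97.6% power; that power is at least 95% for any evaluable number of 102 or more; and that 110 therefore exceeds the minimum. Add a sentence on why 110 was chosen.

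Do not write in a fixed number of successes. The evaluable number is a projection after attrition, and the critical count goes from 10 at n = 110 to 11 at n = 111, where power is 95.5%. A fixed count of 10 could contradict the confidence-limit rule.

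Ask the sponsor to check the original sizing run. Only if it confirms that one-sided 2.5% was intended should the level in section 12.1.2.2, the confidence limit in section 12.1.2.3 (97.5% one-sided) and section 12.4.4 be aligned to it, with power stated as 95.2% at n = 110.

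The cost is a few lines of text, with no additional subjects. The analysis changes only if 2.5% is confirmed.

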12.1.2.3. Statistical Methods

The SMART MSP PAS study's Primary Effectiveness Endpoint will be analyzed when the last 12 Month Visit is completed by the subjects in the LV MSP Group. Subjects eligible for this analysis include all non-responder subjects who meet the definition of the LV MSP Group. The LV MSP Group subjects' CCS data (NYHA class, HF event, all-cause mortality, and patient global assessment) will be collected at the 6 and 12 Month Visit and contribute to the endpoint analysis. The LV MSP Group subjects with the LV MSP on for less than 6 month duration will be included in the analysis.

The 95% one-sided lower pointwise confidence limit of the response rate will be calculated using the one-sided exact methodology for a single binomial proportion and compared to the performance goal of 5%. If the lower confidence limit exceeds the performance goal, then the null hypothesis will be rejected.

Subjects that do not have complete paired CCS data regarding NYHA class, HF event, all-cause mortality, and patient global assessment collected at the 6 and 12 month follow-up visit will be considered to have missing data. A tipping point analysis will be used to determine the potential effects subjects with missing data could have had on the results. The tipping point analysis will consider a range of possible responder rates in the subjects with missing data. The tipping point will be determined by the point at which the endpoint results turn from passing (null hypothesis rejected) to failing (null hypothesis not rejected).

12.2. *Ancillary Assessments*

The ancillary assessments are not formal endpoints and are not statistically powered.

12.2.1. Assessment of Echocardiographic Measurements and CCS Response Status Outcomes in Non-responders

Subjects with echo measurements (such as LVEF and LVESV) at Enrollment, 6, and 12 Month Visit will be reported. In addition, data available (response outcome of CCS and echo

measurements) for these subjects will be reported with summary descriptive statistics and listings. Additional analyses may be explored.

12.2.2. Assessment of Effectiveness of LV MSP in the SMART MSP PAS and SMART Registry

A supplemental analysis of the primary effectiveness endpoint and subgroups will be performed and include a subset of data collected from the SMART Registry, a post market study assessing the LV MSP feature in a similar patient population to fulfill the requirement of an European regulatory body.

12.2.3. Assessment of Worsened LV MSP Group

The percentage of subjects in the LV MSP Group that worsened from the 6 Month Visit through 12 Month Visit will be reported. For this assessment, the CCS will define worsened as “Worsened” only and will not include subjects with a CCS of “No change.”

12.2.4. Assessment of RV-LV Electrical Delay and Response

Available data on RV-LV electrical delay will be collected to determine whether an electrical delay is a predictor of responder status in the overall population.

12.2.5. Assessment of Battery Consumption

In order to understand the impact of MSP on battery longevity, the following time durations will be summarized using descriptive statistics:

- BiV related battery consumption from enrollment to 6 months
- LV MSP related battery consumption from 6 to 12 months
- The average battery life in years for subjects with the LV MSP On at 12 Month Visit

12.2.6. Assessment of SmartDelay and SmartVector Usage

In order to understand the usage of features such as SmartVector and SmartDelay, the following will be summarized using descriptive statistics:

- Percent success using the SmartVector
- Percent use of SmartDelay
- Percent of subjects with SmartDelay value (AV delay and paced chamber) changed between Enrollment Visit and 6 Month Visit and 6 to 12 Month Visit

12.2.7. Assessment of Percentage of Pacing

The following data on percentage of pacing will be summarized using descriptive statistics:

- Percent of BiV pacing at 6 Month Visit
- Percent of LV only pacing (if programmed) at 6 Month Visit

- Percent of LVa and LVb for LV MSP pacing at 12 Month Visit

12.2.8. Assessment of Additional Data Collection

Additional data collection and descriptive statistics will be collected and reported but is not limited to the following data:

- Overall response rate at 6 Month Visit
- Percent of the LV MSP Group subjects with furthest apart two viable vectors

12.3. *Sample Size Summary and Attrition*

The overall sample size of 586 subjects for the required LV MSP Group is based on the Primary Effectiveness endpoint. This sample size accounts for the overall study attrition. Below are the sources of attrition at different stages of this study:

- LV pacing less than 93%⁷: 10%
- Subject exiting the study prior to the 6 Month Visit⁸: 10%
- Responder rate⁹: 70%
- Percent of subjects who cannot achieve 2 viable pacing vectors¹⁰: 15%
- Subject exiting the study between the 6 and 12 Month Visit¹¹: 8%

Figure 12.3-1 indicates the sample size at different time points throughout the study. The overall attrition for this study is 81%.

⁷ Koplan BA, Kaplan AJ, Weiner S, Jones PW, Seth M, Christman SA. Heart failure decompensation and all-cause mortality in relation to percent biventricular pacing in patients with heart failure: is a goal of 100% biventricular pacing necessary? J Am Coll Cardiol. 2009 Jan 27;53(4):355-60.

[figure not shown]
⁸ Based on an estimate from BSC SMART AV Clinical Study and NAVIGATE X4 Clinical Study.

⁹ Based on an evaluation of a set of previous clinical studies reporting clinical response rate to conventional CRT therapy and feedback from the physicians of the study's Steering Committee.

¹⁰ Based on an estimate from BSC NAVIGATE X4 Clinical Study and Rally X4 Clinical Study.

¹¹ Based on an estimate from BSC SMART AV Clinical Study and NAVIGATE X4 Clinical Study.

Figure 12.3-1: Subject Flowchart with Estimated Attrition

12.4. General Statistical Methods

12.4.1. Study Success Criteria

The study will be considered successful if all primary endpoints (safety and effectiveness) are passed.

12.4.2. Analysis Sets

The analysis sets that will be used for each endpoint is shown in **Table 12.4-1**.

Table 12.4-1: Analysis Sets for Each Primary Endpoint

Endpoint	Analysis Sets
SMART MSP PAS Primary Safety Endpoint	All subjects who are non-responders with the LV MSP on for any duration from the 6 to the 12 month visit
SMART MSP PAS Primary Effectiveness Endpoint	All subjects who meet the LV MSP group criteria

12.4.3. Control of Systematic Error/Bias

Selection of patients will be made from the Investigator’s usual patient population. All patients meeting the eligibility criteria and having signed the ICF will be enrolled in the study. To control for inter-observer variability among sites, an independent Clinical Events Committee (CEC) will adjudicate the reported HF event to be used as the component of the CCS to assess the Primary Effectiveness Endpoint.

12.4.4. Control of Type I Error

Each primary endpoint can be tested at the significance level of 5% while still maintaining the overall type I error level at no greater than 5%. This follows the methodology of the Intersection-Union Test (IUT).

12.4.5. Number of Subjects per Investigative Site

To avoid any center effect and bias, one center will not be authorized to enroll more than 20% of the study subjects.

12.5. Data Analyses

In addition to the study endpoint analysis discussed in **Section 12.1** and **Section 12.2**, the following data analyses are planned for the SMART MSP Study.

12.5.1. Interim Analyses

No formal interim analyses are planned for the purpose of stopping the study early for declaring effectiveness or for futility. Analysis of each endpoint will be performed when all applicable data for that endpoint has been collected.

12.5.2. Pooling Analysis

Assessment of Pooling Across Investigational Centers

The poolability of data by center will be tested. This analysis will be performed to determine whether there are differences from center-to-center.

Center-to-center heterogeneity will be assessed by performing random effects logistic regression analysis.

Investigational center will be added into the model as a random effect. Centers will be deemed to be heterogeneous if the variance of the random center effect is found to significantly differ from zero. A significance level of 15% will be used for each test.

12.5.3. Subgroup Analyses

Analyses will be performed for the primary effectiveness endpoint to determine whether significant differences exist in endpoint results between subgroups of the LV MSP Group. The list of baseline covariates (with applicable subgroups in parentheses) includes, but is not necessarily limited to:

Categorical variables:

- Ischemic Etiology (Ischemic vs Non-Ischemic)
- Bundle Branch Block morphology (LBBB vs Non-LBBB)
- NYHA class (I/II vs III/IV)

- LV MSP Pacing chamber (BiV MSP vs. LV ONLY MSP)¹²
- Presence of atrial fibrillation (Yes or No)
- Diabetes (Yes vs. No)
- Sex (Male vs. Female)
- Spiral LV lead length (Short vs. Long)
- LV lead shape (Spiral vs. Straight)

Continuous Variables:

- RV-LV electrical delay
- Electrode spacing between the two LV pacing vectors¹³
- QRS width

For categorical variables, the subgroup variable will be added to a logistic univariate regression model. In addition, continuous variables will be determined as binary or continuous by linearity characteristics and/or clinical determination. If deemed as continuous, the subgroup variable will be added to a logistic univariate regression model.

In addition to subgroup analyses, descriptive statistics of patient demographic and baseline characteristics will be presented for each subgroup listed in this section. Descriptive statistics will also be presented for the overall study population.

12.5.4. Multivariable Analyses

As stated in the subgroup analysis in **Section 12.5.3**, the number of events in the LV MSP Group is limited. Therefore, multivariate analyses will be deemed exploratory. The various baseline covariates and their relationship to effectiveness endpoint are outlined in **Section 12.5.3**. For the effectiveness endpoint and subgroup analyses, all baseline characteristics found to be significantly associated with the response status will be included as covariates, in a multivariate regression model. The impact of each baseline characteristic's subgroups will be presented along with the multivariate model results.

12.5.5. Changes to Planned Analyses

Any changes to the planned statistical analyses made prior to performing the analyses will be documented in a Statistical Analysis Plan approved prior to performing the analyses. Changes from the planned statistical methods after performing the analyses will be documented in the clinical study report along with a reason for the deviation.

¹² LV MSP pacing chamber is only collected at the 6 Month Visit when the LV MSP feature is turned on.

¹³ Electrode spacing between the two LV pacing vectors is only collected at the 6 Month Visit when the LV MSP feature is turned on.

13. Data Management

13.1. Data Collection, Processing, and Review

Subject data will be recorded in a limited access secure electronic data capture (EDC) system.

The clinical database will reside on a production server hosted by EDC System. All changes made to the clinical data will be captured in an electronic audit trail and available for review by the sponsor or its representative. The associated RAVE software and database have been designed to meet regulatory compliance for deployment as part of a validated system compliant with laws and regulations applicable to the conduct of clinical studies pertaining to the use of electronic records and signatures. Database backups are performed regularly.

The Investigator provides his/her electronic signature on the appropriate electronic case report forms (eCRFs) in compliance with local regulations. A written signature on printouts of the eCRFs must also be provided if required by local regulation. Changes to data previously submitted to the sponsor require a new electronic signature by the Investigator acknowledging and approving the changes.

Visual and/or electronic data review will be performed to identify possible data discrepancies. Manual and/or automatic queries will be created in the EDC system and will be issued to the site for appropriate response. Site staff will be responsible for resolving all queries in the database.

